# 3. Secondary Efficacy Analyses at Secondary Endpoints (Long-Term Follow-up)

Efficacy of outcome measures for long-term follow-up will be assessed at baseline, midpoint (visit 9), primary endpoint (visit 16), 3-month follow-up (visit 17), and 6-month follow-up (Visit 18) to examine changes over time in the total sample, and separately, by PTSD+ participants and CSO participants.

For each model, a one-way repeated-measures ANCOVA with baseline scores as covariates and post-hoc contrast comparisons will be conducted to test the effects of the treatment on: PTSD CAPS-5; Significant Others' Responses to Trauma Scale (SORTS); Posttraumatic Stress Disorder Checklist for the DSM-5 (PCL-5); Beck Depression Inventory-II (BDI-II); Emotion Regulation Questionnaire (ERQ); Pittsburgh Sleep Quality Index (PSQI); Posttraumatic Growth Inventory (PTGI); Toronto Alexithymia Scale-20 (TAS-20); Inventory of Psychosocial Functioning (IPF); Revised Conflict Tactics Scale (CTS-2); Trauma and Attachment Beliefs Scale (TABS); and Multiscale Dissociation Inventory (MDI). Relationship distress outcome measures include: Interpersonal Reactivity Index (IRI); Quality of Relationships Inventory (QRI); Miller Social Intimacy Scale (MSIS); Interpersonal Closeness Measure (IPC); and Couples Satisfaction Index (CSI).

If data is missing from participant dropouts a mixed effect model repeat measures (MMRM) will be used instead of an ANCOVA.

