3.2 Secondary Objectives

Secondary and exploratory objectives are to assess changes in the dyad's relationship functioning at the Midpoint and Primary Endpoints, assess changes in self- and CSO participant-reported PTSD symptoms in the PTSD+ participant, and assess problems that often co-occur with PTSD, such as depression, sleep disturbances, maladaptive beliefs about self and others, and emotion regulation difficulties.

- Assess changes in PTSD symptoms from baseline as measured by the CAPS in participants with chronic PTSD at Long-term Follow-up at 3 months and 6 months.
- Assess changes in self-reported PTSD symptoms from baseline as measured with the Posttraumatic Stress Disorder Checklist for the DSM-5 (PCL-5) at Baseline, at each Integrative Session, at the Midpoint, Primary Endpoint and Long-term Follow-up at 3 months and 6 months for both the PTSD+ participant and CSO participant (based on the (PTSD+ participant).
- Assess changes in depression symptoms from baseline with the Beck Depression Inventory-II (BDI-II) at Baseline, Midpoint, the Primary Endpoint, and Long-term Follow-up at 3 months and 6 months for both participants.
- Assess changes in self-reported sleep quality from baseline with the Pittsburgh Sleep Quality Index (PSQI) at Baseline, Midpoint, the Primary Endpoint, and Long-term Follow-up at 3 months and 6 months for both participants.
- Assess changes in self-reported posttraumatic growth from baseline with the Posttraumatic Growth Inventory (PTGI) by the PTSD+ participant and CSO participant (based on the PTSD+ participant) at the Midpoint, the Primary Endpoint, and Long-term Follow-up at 3 months and 6 months.
- Assess changes in psychological and physical aggression from baseline with the

- Revised Conflict Tactics Scale (CTS-2) at the Midpoint, Primary Endpoint, and Long-term Follow-up at 3 months and 6 months for both participants.
- Assess changes in emotional regulation from baseline with the Emotion Regulation Questionnaire (ERQ) at the Midpoint, Primary Endpoint, and Longterm Follow-up at 3 months and 6 months for both participants.
- Assess changes in compassion, empathy, and social functioning from baseline
 with the Interpersonal Reactivity Index (IRI) on the day after each Experimental
 Session, at Midpoint, Primary Endpoint, and Long-term Follow-up at 3 months
 and 6 months for both participants.

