#### PTSD+ Participants Only

[figure not shown]
• Assess changes in PTSD symptoms from baseline as measured by the CAPS-5 in participants with chronic PTSD at Long-term Follow-up at 3 months and 6 months.

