#### CSO Participants Only

• Assess changes in partner accommodation from baseline with the Significant Others' Responses to Trauma Scale (SORTS) at the Midpoint, Primary Endpoint, and Long-term Follow-up at 3 months and 6 months for the CSO participant.

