## PTSD+ Participants and CSO Participants

 Assess changes in self-reported PTSD symptoms from baseline as measured with the Posttraumatic Stress Disorder Checklist for the DSM-5 (PCL-5) at Baseline, at each Integrative Session, at the Midpoint, Primary Endpoint and Long-term Follow-up at 3 months and 6 months for both the PTSD+ participant and CSO participant (based on the

[figure not shown]

(PTSD+ participant).

- Assess changes in depression symptoms from baseline with the Beck Depression Inventory-II (BDI-II) at Baseline, Midpoint, the Primary Endpoint, and Long-term Follow-up at 3 months and 6 months for both participants.
- Assess changes in emotional regulation from baseline with the Emotion Regulation Questionnaire (ERQ) at the Midpoint, Primary Endpoint, and Long-term Follow-up at 3 months and 6 months for both participants.
- Assess changes in self-reported sleep quality from baseline with the Pittsburgh Sleep Quality Index (PSQI) at Baseline, Midpoint, the Primary Endpoint, and Long-term Follow-up at 3 months and 6 months for both participants.
- Assess changes in self-reported posttraumatic growth from baseline with the Posttraumatic Growth Inventory (PTGI) by the PTSD+ participant and CSO participant (based on the PTSD+ participant) at the Midpoint, the Primary Endpoint, and Long-term Follow-up at 3 months and 6 months.
- Assess changes in emotion recognition and alexithymia from baseline with the Toronto Alexithymia Scale-20 (TAS-20) at the Midpoint, Primary Endpoint, and Long-term Follow-up at 3 months and 6 months for both participants.
- Assess changes in psychosocial functioning from baseline with the Inventory of Psychosocial Functioning (IPF) at the Midpoint, Primary Endpoint, and Long-term Follow-up at 3 months and 6 months for both participants.
- Assess changes in psychological and physical aggression from baseline with the Revised Conflict Tactics Scale (CTS-2) at the Midpoint, Primary Endpoint, and Long-term Follow-up at 3 months and 6 months for both participants.
- Assess changes in trauma-related beliefs from baseline with the Trauma and Attachment Beliefs Scale (TABS) at the Midpoint, Primary Endpoint, and Long-term Follow-up at 3 months and 6 months for both participants.
- Assess changes in dissociative symptomology from baseline with the Multiscale Dissociation Inventory (MDI) at the Midpoint, Primary Endpoint, and Long-term Follow-up at 3 months and 6 months for both participants.

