#### Relationship Outcomes

- Assess changes in compassion, empathy, and social functioning from baseline with the Interpersonal Reactivity Index (IRI) on the day after each Experimental Session, at Midpoint, Primary Endpoint, and Long-term Follow-up at 3 months and 6 months for both participants.
- Assess changes in relationship satisfaction from baseline with the Quality of Relationships Inventory (QRI) at the Midpoint, Primary Endpoint, and Long-term Follow-up at 3 months and 6 months for both participants.
- Assess changes in social intimacy from baseline with the Miller Social Intimacy Scale
  (MSIS) at the Midpoint, Primary Endpoint, and Long-term Follow-up at 3 months and 6
  months for both participants.
- Assess changes in interpersonal closeness from baseline with the Interpersonal Closeness Measure (IPC) during Experimental Sessions, at the Midpoint, Primary Endpoint, Long-

term Follow-up at 3 months and 6 months for both participants.

• Assess changes in couples satisfaction from baseline with the Couples Satisfaction Index (CSI) at the Midpoint, Primary Endpoint, and Long-term Follow-up at 3 months and 6 months for both participants if romantically involved.

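### The SAP's long-term follow-up ANCOVA makes baseline both a time point and the covariate; read in the ordinary way, it compares follow-up visits with each other and leaves change from baseline at visits 17 and 18 untested

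*SAP*

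**What the plan says.** The SAP's long-term analysis (Efficacy Analyses, item 3) opens: "Efficacy of outcome measures for long-term follow-up will be assessed at baseline, midpoint (visit 9), primary endpoint (visit 16". The list runs on to visits 17 and 18, and the purpose given is to examine change over time. The next paragraph sets the model for 17 measures: a "one-way repeated-measures ANCOVA with baseline scores as covariates and post-hoc contrast comparisons will be conducted". If there are dropouts: "If data is missing from participant dropouts a mixed effect model repeat measures (MMRM) will be used instead of an ANCOVA". The SAP does not say how that mixed model handles baseline.

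The objectives are changes from baseline. For CAPS-5 in the SAP: "Assess changes in PTSD symptoms from baseline as measured by the CAPS-5", at 3 and 6 months. In protocol section 3.2: "Assess changes in PTSD symptoms from baseline as measured by the CAPS in participants with chronic PTSD at Long-term Follow-up". SAP section 3.2 words the other 16 measures as changes from baseline too.

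Protocol section 12.0 assigns durability to mixed-effects regression on changes from baseline to the three- and six-month assessments. SAP section 1.0 says the SAP is based on the protocol's analysis plan.

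**The concern.** With a single group, time is the only factor and change over time is the only question. A baseline covariate usually serves to sharpen a comparison between groups, and there is none here. If baseline becomes the covariate, it normally leaves the set of outcome visits, and what remains is a comparison among post-treatment visits.

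At stake is the durability result. A lasting gain would look null. A significant result would point to movement between follow-up visits, which includes loss of benefit. A reader told that the long-term test was significant could take the wrong message from it.

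**Working it through.** **1. The plan's own figure.** Protocol section 12.1 gives a within-subject effect of 0.8, n=10, two-sided 0.05 and power of 62%. The noncentrality is 0.8 × √10 = 2.530 on 9 df. The noncentral t gives 61.6%, so the figure reproduces.

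**2. What the ANCOVA tests.** Take baseline B as covariate only, with a common slope:

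Y_ij = μ_j + βB_i + p_i + e_ij, for j = visits 16, 17, 18.

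Then Y_i18 − Y_i16 = (μ_18 − μ_16) + (e_i18 − e_i16). The term βB_i has cancelled. The time test is of μ_16 = μ_17 = μ_18. If the improvement is the same size at all three visits, that hypothesis is true whatever the size, so the rejection rate equals alpha. For measures collected at visit 9, that visit joins the set; baseline still does not.

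**3. Simulation inputs.** The documents give no CAPS-5 SD or correlation, so these are assumptions: baseline mean 30 or 40; baseline SD 8; follow-up SD 8 or 12; equal correlations 0.3, 0.5, 0.7, or AR(1) 0.5, 0.7, 0.8, or 0.3 with baseline and 0.8 among follow-ups. That is 2 × 2 × 7 = 28 scenarios, with 20,000 trials each and n=10. The change is 0.8 times the SD of visit 18 minus baseline. For SD 8 and 8 with r=0.7 it is 0.8 × √(64 + 64 − 89.6) = 4.96 points; the largest is 10.85.

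**4. Rejection rates.**

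| True pattern | Ordinary ANCOVA, visits 16 to 18 (F on 2, 18 df) | Paired contrast, visit 18 against baseline |
|---|---|---|
| No change | 4.7 to 6.0% | 4.8 to 5.3% |
| Sustained 0.8 | 4.7 to 6.0% | 60.8 to 62.4% |
| Fading 0.8, 0.6, 0.4 | 13.5 to 48.6% | not reported |

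With visit 9 included and equal SDs, the ANCOVA rejects 5.1 to 6.7% at a sustained 0.8.

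A separate simulation (equal correlations 0.3, 0.5, 0.7; 2,000 trials each) agrees. The common-slope time test rejects 5.0 to 5.2% with no change, 5.4 to 5.6% at a sustained 0.8, and 4.3 to 5.2% at a sustained 1.5. With effects of 1.5, 0.75 and 0 at visits 16, 17 and 18, which is full relapse, it rejects 97.8 to 98.3%.

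**5. The other reading: baseline kept as an outcome level and as covariate, with visit-specific slopes, centred.** The contrast estimates the mean change, but its standard error treats baseline as fixed. With equal SDs and correlation r, the residual variance over the variance of change is (1 − r²)/[2(1 − r)] = (1 + r)/2. At r=0.5 this is 0.75, so the standard error is √0.75 = 0.866 of what it should be. Simulated false rejection of the visit 18 contrast is 4.9 to 12.3% over the 28 scenarios. In the separate simulation the overall time test gives 5.8 to 8.4%.

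**6. Planned tests and how far they reach.**

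| Source | Test | Times |
|---|---|---|
| SAP item 1 | Paired t-test, CAPS-5 | Baseline, visit 16 |
| SAP item 2 | Repeated-measures ANOVA, no covariate | Baseline, visits 9, 16 |
| SAP item 3 | ANCOVA above | Through visit 18 |
| SAP item 4 | Correlations between dyad members | Through visit 18; not a test of change |
| Protocol 12.0 | Mixed-effects regression | Change from baseline at 3 and 6 months |

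**7. CAPS-5 at visit 9.** SAP items 2, 3 and 4 pair CAPS-5 with visit 9. Protocol Tables 3 and 4, protocol section 5.2.7 and SAP Table 3 show no CAPS there.

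**The case against.** The strongest reply is that the SAP does list baseline as a time point and leaves the contrasts open, so an analyst could compare visits 17 and 18 with baseline. That stands as far as it goes: the failure depends on the ordinary reading of ANCOVA. But a valid baseline contrast needs choices that the SAP does not state, and the centred version in step 5 has a standard error that is too small.

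Second, the protocol already plans the right comparison, and SAP section 4.0 calls the protocol the definitive reference. The first part stands. The sentence in 4.0, however, introduces the design overview, and the SAP's analysis section brings in a mixed model only after dropouts. Protocol section 12.0 also names repeated-measures ANCOVA for the self-report measures, but it does not make baseline the covariate and it gives durability to mixed models.

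Third, these aims are secondary or exploratory in a study not meant for registration, and the SAP is to be final before any analysis. That limits the consequence.

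A reader might infer more than the documents support:

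- That no planned test reaches visits 17 and 18. The table in step 6 shows otherwise.
- That false-positive rates are very high. An uncentred covariate gave up to 59% in one scenario, but the SAP never specifies such a fit.
- That pooling the error across visits is a fault of this ANCOVA. If pooled error were used, the covariate-free ANOVA in item 2 would share the problem (8 to 9% false rejection with three visits under AR(1) or unequal correlations). The SAP does not state the error term.
- That CAPS-5 at visit 9 would give a wrong result. No data exist there to analyse.

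**Conclusion.** Wrong as written, with consequences for secondary and exploratory aims only. The SAP gives baseline two roles in a one-group model and does not define the contrasts. On the ordinary ANCOVA reading, its only test of change over time through visits 17 and 18 does not address the change-from-baseline objectives and departs from protocol section 12.0.

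The insensitivity to a sustained effect (about 5% against about 62%) follows from the algebra and held at every correlation and SD tried. The 14 to 49% for fading benefit and the 5 to 12% for the centred alternative rest on the assumed SDs and correlations and are not bounds. The primary paired t-test, the descriptive statistics and Hedges' g are not affected.

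**What to change.** In SAP Efficacy Analyses item 3, strike the words that make baseline scores covariates and keep baseline as an outcome visit. Name the contrasts: visits 16, 17 and 18 each against baseline, plus visit 9 for measures collected there. Test each with its own error, as a paired t-test on change from baseline, and not with an error pooled under compound symmetry.

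Where data are missing, use the mixed model of protocol section 12.0 with baseline in the response, categorical visit, unstructured covariance and a small-sample degrees-of-freedom method such as Kenward-Roger. Fall back to the paired contrasts if it does not converge. Fit it separately for PTSD+ and CSO participants, or account for dyad in the total sample.

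Checks on this repair: with complete data, the mixed-model contrast and the paired t-test gave the same p-value (0.4919 on 9 df). With 2 or 3 of 10 lost at random, false rejection was 5.5 to 6.9% with Kenward-Roger, 9 to 12% with no df method and 5.0 to 5.8% for the paired fallback (1,500 trials per case). These runs used four visits, no dyad clustering and no carried-forward values, which is why the paired contrasts should lead.

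The cost is SAP wording and programming; no assessment is added. Power is about 62% at an effect of 0.8 with complete data. With two dropouts it is about 52 to 59% for the mixed model or 48 to 50% for the paired contrast.

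Minor separate edit: for CAPS-5, use baseline and visits 16 to 18 in item 3, remove it from item 2, where without visit 9 it only repeats the primary test, and drop the visit 9 CAPS-5 correlations in item 4.

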# 4. Additional Exploratory Analysis

Pearson Correlations will be computed between PTSD+ participants' CAPS-5 scores and CSO participants' outcomes (all) [4]. This analysis will be conducted for baseline, midpoint (visit 9), primary endpoint (visit 16), 3-month follow-up (visit 17), and primary endpoint (visit 18). Correlations (*r*) and *p* values will be reported to assess the direction and magnitude of these relationships. This analysis is intended to explore the potential impact of CSO participants' responses to the given treatment on PTSD+ participants' CAPS-5 scores over time.

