5.0 Methods

5.1 Measures

The following outcome, safety, and process measures will be used in the study. This study will utilize methods described in the Treatment Manual for conducting MDMA-assisted Psychotherapy combined with methods from the CBCT for PTSD manual. The integration of these manuals will provide the researcher with a consistent psychotherapy approach and test an investigational form of drug-assisted psychotherapy. The Treatment Manual is not intended to define all interactions that occur in the therapy. All psychotherapy sessions, including Experimental Sessions, may be recorded to audio and video, with all recordings preserved for research and training purposes.

Page 32 of 89

Table 4: Study Measures

Measure	Purpose	Administration	Time/ # of items	When	PTSD+ Participant	CSO Participant
Screening, Inclusion & Exclusion						
SCID for DSM-5- AXIS 1 only and then screening question for AXIS 2 modules (do modules if needed)	Screening	Interview	60 minutes	Baseline	Y	Y
Primary & Secondary Outcomes						
CAPS-5 Clinician Administered PTSD Scale for DSM-5	PTSD Severity	Interview	90 minutes	Baseline, Endpoint, LTFU 3, 6	Y	N
PCL (last month) PTSD Checklist for DSM-5	PTSD symptoms	Self-report	10-15 minutes	Baseline (with LEC), Endpoint, LTFU 3, 6	Y	Y (PCL- Participant)
PCL (since last visit) PTSD Checklist for DSM-5	PTSD symptoms	Self-report	10-15 minutes	Integrative Sessions, Midpoint	Y	Y (PCL- Participant)
PCL (since last week) PTSD Checklist for DSM-5	PTSD symptoms	Self-report	10-15 minutes	Visit 2	Y	Y (PCL- Participant)
BDI-II Beck Depression Inventory	Depression Symptoms	Self-report	5-10 minutes	Baseline, Midpoint, Endpoint, LTFU 3, 6	Y	Y
ERQ Emotional Regulation Questionnaire	Emotion regulation	Self-report	4-6 minutes	Baseline, Midpoint, Endpoint, LTFU 3, 6	Y	Y
IRI Interpersonal Reactivity Index	Compassion empathy, social functioning	Self-report	10 minutes	Baseline, Day after Experimental Sessions, Midpoint, Endpoint, LTFU 3, 6	Y	Y
PSQI Pittsburg Sleep Quality Index	Sleep Quality	Self-report	5-10 minutes	Baseline, Midpoint, Endpoint, LTFU 3, 6	Y	Y
PTGI Post Traumatic Growth Inventory	Growth after Trauma	Self-report	5-10 minutes	Baseline, Midpoint, Endpoint, LTFU 3, 6	Y	Modified for participant. Participant will rate the PTSD participant. Y
TAS-20 Toronto Alexithymia Scale	Emotion recognition, alexithymia	Self-report	5 minutes	Baseline, Midpoint, Endpoint, LTFU 3, 6	Y	Y

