The secondary measure of PTSD symptoms will be the PCL (reported for last month, since last visit, and since last week per Table 4), a self-report measure designed to follow DSM-5 criteria for assessing PTSD. The PTSD Checklist (PCL-5) [137] is a 20-item selfreport questionnaire in which respondents indicate the presence and severity of PTSD symptoms, derived from the DSM-5 symptoms of PTSD [36]. Participants indicate how much distress they have experienced due to symptoms such as "Repeated, disturbing memories, thoughts, or images of a stressful experience from the past," "Trouble remembering important parts of a stressful experience from the past," and "Feeling irritable or having angry outbursts" on a five-point Likert-type scale (1 = not at all, 5 = extremely). The total PCL-5 score (a sum of all 20 items) provides an index of overall PTSD symptom severity. Reports on reliability and validation of the PCL-5 are underway; preliminary comparison with the PCL for DSM IV suggests that the cut-off for PCL-5 is 11 to 14 points lower than for the PCL [137]. Participants will complete the PCL-5 questionnaire, as specified in Table 3: Time and Events. The PTSD+ participant will complete it based on their own symptoms and the CSO participant will complete it based on the PTSD+ participant.

The BDI-II is a 1996 revision of the BDI, a 21-item self-report measure [138, 139] that will serve as a measure of depression according to DSM-IV criteria [140]. The BDI-II has been validated, has high internal consistency and good test/re-test reliability, and is not overly sensitive to daily variations in mood. It takes five to ten minutes to complete [140]. Score cutoffs indicate: 0-13 minimal depression, 14-19 mild depression, 20-28 moderate depression, and 29-63 severe depression. Initial and subsequent studies report that the BDI-II total score has a reliability coefficient of 0.90 to 0.91 and that it is related to other measures of depression symptoms [140, 141]. Higher scores indicate more severe depressive symptoms. Both the participants will complete the BDI-II according to Table 3: Time and Events.

The ERQ is a brief measure of self-reported emotion-regulation. It consists of ten items that is intended to assess means of coping with emotions via changing them, as through reappraisal, or suppressing them [142]. Respondents rate indicate the extent of their

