The Trauma and Attachment Beliefs Scale (TABS) was developed as a brief self-report measure of maladaptive beliefs about current life circumstances that may occur following trauma exposure [167]. The measure consists of 15 items, with responses made on a seven-point Likert scale with 1 = not at all true for you and 7 = completely true for you. This scale assesses maladaptive beliefs within three domains: (a) threat of harm, (b) self-worth and judgment, and (c) reliability and trustworthiness of others. After following procedures for reverse-scored items, scores are summed to produce scale scores for each domain. The TABS has an overall reliability of alpha of 0.82, with scale reliability ranging from 0.71 to 0.76. TABS scores exhibit a positive association with CAPS global severity scores, particularly for the Threat of Harm scale, and the scale had a negative association with scores on the PTGI. Both the PTSD+ participant and the CSO participant will complete the TABS according to Table 3: Time and Events. The CSO participant will complete a modified version.

The Multiscale Dissociation Inventory (MDI) is a 30-item self-report test of dissociative symptomatology in the last month, with responses made along a five-point Likert scale, with 1 = never and 5 = very often. It is fully standardized and normed, and measures six different type of dissociative response: disengagement, depersonalization, derealization, emotional constriction / numbing, memory disturbance, and identity dissociation. A total

dissociation score can also be calculated. Reliability for each subscale various from 0.74 for memory disturbance to 0.91 for derealization. The MDI has been found to have good psychometric qualities in both the normative and validation samples [168-170]. Both the PTSD+ participant and the CSO participant will complete the MDI according to Table 3: Time and Events.

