A blinded IR who will not be present during any of the therapy sessions will administer:

• Structured Clinical Interview for DSM-5 Diagnoses (Research Version) (SCID-RV) to assess eligibility based on Axis I diagnoses, which includes a self-report questionnaire to focus on modules to use based on symptoms for both the PTSD+participant and CSO participant

Page 43 of 89

- SCID-II Axis 2 questionnaire to determine if specific modules of the SCID-II Interview will be conducted to confirm diagnoses of personality disorders
- Last-month CAPS for the PTSD+ participant to assess PTSD symptoms and eligibility, which may be recorded to video in as many instances as necessary to establish inter-rater reliability

The following self-report measures will be completed:

- PTGI (in reference to time since the trauma) for the PTSD+ participant and modified for the CSO participant to rate the PTSD+ participant
- PCL-5 (last month) to assess PTSD symptoms for the PTSD+ participant and modified for the CSO participant to rate the PTSD+ participant.
- TABS to assess trauma related beliefs for the PTSD+ participant and modified for the CSO participant to rate the PTSD+ participant
- MDI to assess dissociative symptomology for the PTSD+ participant and CSO participant
- SORTS to assess partner accommodation for the CSO participant
- BDI-II to assess depression symptoms for both the PTSD+ participant and CSO participant
- PSQI to assess sleep quality for both the PTSD+ participant and CSO participant. PSQI-PTSD Addendum will be assessed for the PTSD+ participant only
- ERQ to assess emotional regulation for both the PTSD+ participant and CSO participant
- TAS-20 to assess emotion recognition, alexithymia for both the PTSD+ participant and CSO participant
- QRI to assess relationship satisfaction for both the PTSD+ participant and CSO participant
- CTS to assess conflict, tactics and aggression for both the PTSD+ participant and CSO participant
- IPF to assess psychosocial functioning for both the PTSD+ participant and CSO participant
- MSIS to assess social intimacy for both the PTSD+ participant and CSO participant
- IRI to assess compassion, empathy and social functioning for both the PTSD+ participant and CSO participant
- IPC for both the PTSD+ participant and CSO participant
- CSI for both the PTSD+ participant and CSO participant, if in a romantic relationship

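### The SAP's correlations of CAPS-5 with all CSO outcomes include forms on which the CSO rates the PTSD+ participant (PCL-5, PTGI and, per the visit sections, TABS), so these cannot show the CSO's own response

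*SAP*

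**What the plan says.** SAP, 4. Additional Exploratory Analysis: "Pearson Correlations will be computed between PTSD+ participants' CAPS-5 scores and CSO participants' outcomes (all", at baseline, visit 9, visit 16 and both long-term follow-ups, with r and p reported. The analysis is "intended to explore the potential impact of CSO participants' responses to the given treatment on PTSD+ participants' CAPS-5 scores over time". No CSO-completed form is excluded or set apart.

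Who is rated on three of those forms:

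- **PCL-5.** Protocol 5.1.1: "the CSO participant will complete it based on the PTSD+ participant".
- **PTGI.** Protocol Table 4, CSO column: "Modified for participant. Participant will rate the PTSD participant". The visit sections agree.
- **TABS.** Protocol 5.2.1: "TABS to assess trauma related beliefs for the PTSD+ participant and modified for the CSO participant to rate the PTSD+ participant". Sections 5.2.7, 5.2.8 and 5.2.9 say the same. The TABS paragraph in 5.1.1 is less specific: "The CSO participant will complete a modified version". Table 4 also says only that the CSO form is modified, and the TABS objective in protocol 3.2 says nothing about who is rated.

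SAP 3.2 names CSO-reported symptoms of the PTSD+ participant among its aims and marks the PCL-5 and PTGI objectives as based on the PTSD+ participant. The TABS objective carries no such note: "Assess changes in trauma-related beliefs from baseline with the Trauma and Attachment Beliefs Scale (TABS"), listed for both participants.

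The SAP's efficacy sections 2 and 3 then analyse all three instruments in the total sample and separately for PTSD+ and CSO participants, without separating informant ratings from self-ratings.

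**The concern.** A correlation can speak to the CSO's response to treatment only if the CSO-side variable measures the CSO, or the relationship as the CSO experiences it. A CSO's rating of the patient's symptoms, growth or beliefs is an informant measure of the patient. Correlating it with CAPS-5 compares two views of one person.

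For PCL-5 the overlap is nearly complete in content. Both instruments follow the DSM-5 symptoms of PTSD, and at the four visits that have a CAPS-5 both refer to the last month (Table 4 and protocol 5.1.1). Agreement between CSO and rater would produce a correlation even if nothing had changed in the CSO. Under the purpose the SAP states, that correlation could be read as an influence of the CSO's response on the patient.

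The same gap affects the SAP's sections 2 and 3. A change on these forms would be tabulated under CSO participants when it is a change the CSO perceives in the patient. The total-sample models would combine a self-rating and an informant rating of the same patient as if they were results for two people. Change scores or a multiplicity adjustment would not repair this, because the variable itself is not a CSO response.

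**Working it through.** **Plan's own figure.** The documents give none for these correlations. Their only power figure, 62% for the paired comparison of CAPS (10 participants, effect size 0.8, two-sided 0.05; protocol 12.1), reproduces: noncentral t, 9 df, noncentrality 0.8 × √10 = 2.53, power 61.6%. This point does not depend on it.

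**Forms affected.** Table 4 gives the CSO 16 outcome instruments: PCL-5, BDI-II, ERQ, IRI, PSQI, PTGI, TAS-20, QRI, SORTS, CTS-2, IPF, MSIS, TABS, MDI, IPC and CSI. Three (PCL-5, PTGI, TABS) rate the patient if the visit sections are followed: 3/16 = 19%.

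**Correlations affected.** CAPS-5 is scheduled at four visits (baseline, primary endpoint, 3 and 6 months). The SAP also lists the midpoint for this analysis, but no midpoint CAPS-5 is scheduled. Taking one score per instrument:

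- total: 16 × 4 = 64
- informant ratings: 3 × 4 = 12
- remainder: 64 − 12 = 52
- PCL-5 alone: 1 × 4 = 4

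One score per instrument is a simplification. The ERQ gives two scales and the IPC several distances, so the true total is larger.

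**How often agreement alone reaches p≤0.05.** Inputs: n = 10 dyads; two-sided 0.05 (SAP 6.0). The critical correlation is

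r_crit = t / √(n − 2 + t²), with t = t(0.975; 8 df) = 2.306

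r_crit = 2.306 / √(8 + 5.318) = 0.632.

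Bivariate normal samples of 10 pairs were simulated (200,000 per row), counting |r| ≥ 0.632. The true correlation ρ stands for agreement about the patient, with no contribution from any change in the CSO. Its values are assumptions; neither document gives one.

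| Assumed ρ | Share with p≤0.05 |
|---|---|
| 0 | 5% |
| 0.3 | 13% |
| 0.5 | 33% |
| 0.7 | 68% |
| 0.8 | 87% |

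These shares are for one correlation at one visit. They bear on PCL-5, where the two instruments cover the same symptoms in the same patient. PTGI (growth) and TABS (beliefs) also rate the patient but measure other constructs, so the documents give no reason to place them on the same scale.

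**SORTS.** Protocol 5.1.1 also has this completed about the PTSD+ participant, but what it captures is the partner's accommodation and distress. That is a CSO response, so it is not counted among the three.

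**The case against.** The strongest reply is that the SAP already knows two of the three forms are informant ratings: its objectives say so, and SAP 4.0 makes the protocol the definitive reference. A reader might infer that the SAP overlooks the distinction or would report these scores as benefit to the CSO. The documents do not support that: the objectives mark PCL-5 and PTGI, and no analysis section calls the scores CSO benefit. What stands is narrower. The analysis sections do not carry the note through, and the correlation section takes in every CSO outcome under a purpose these forms cannot serve.

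Second, TABS is not settled. Four visit sections say the CSO rates the patient; protocol 3.2, Table 4 and the TABS paragraph in 5.1.1 do not say who is rated. The SAP objective follows protocol 3.2, so the gap begins in the protocol. This objection stands. Protocol 5.1.1 also calls the CSO's TAS-20 modified without explanation, so the count of three may not be final.

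Third, a reader might apply the upper percentages to all 12 informant correlations, or take a significant PCL-5 result as assured. Neither follows. The percentages depend on an assumed ρ and concern 4 of the 64 correlations. At ρ = 0.5 two studies in three would not reach significance. At baseline every PTSD+ participant must meet CAPS diagnostic criteria, which may narrow the CAPS-5 range and lower the correlation.

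Finally, the analysis is exploratory, in a feasibility study not meant to lead to registration. That limits the weight of the point. It does not make the stated interpretation valid, and SAP 2.0 says the results will help design a larger study.

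**Conclusion.** The point holds in a limited form. The SAP's correlation analysis includes the CSO-completed PCL-5 and PTGI, and the TABS if the visit sections are right. Those forms rate the PTSD+ participant and cannot show the impact of the CSO's own response. Sections 2 and 3 share the fault through their CSO and total-sample analyses.

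The scope is 3 of 16 CSO instruments, or 12 of 64 correlations at one score per instrument and four CAPS-5 visits; with TABS left aside as unresolved, it is 2 of 16 and 8 of 64. For PCL-5 alone, agreement about the patient would give p≤0.05 in about 13% to 87% of studies of 10 dyads, for an assumed ρ of 0.3 to 0.8, against 5% with no correlation. No such figure is claimed for PTGI or TABS.

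This is a correction to exploratory analyses. The primary CAPS-5 comparison is unaffected.

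**What to change.** - **SAP section 4.** Limit the CSO-response correlations to measures on which CSOs rate themselves or the relationship; SORTS stays in. Report the CSO-completed PCL-5, PTGI and TABS separately as informant ratings of the PTSD+ participant, set against the CAPS-5 as agreement.
- **SAP sections 2 and 3.** Label these forms as informant-rated outcomes of the PTSD+ participant, and do not pool them with self-ratings in the total-sample models.
- **TABS.** Reconcile protocol 3.2, Table 4 and 5.1.1 with 5.2.1, 5.2.7, 5.2.8 and 5.2.9. If the visit sections are confirmed, add to the SAP's TABS objective the same note that PCL-5 and PTGI carry, that the CSO's rating is based on the PTSD+ participant. If they are not, TABS returns to the CSO set.
- **TAS-20.** State in what way the CSO form is modified, so that the list of informant forms is complete.

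The cost is SAP and protocol wording and table labels. No new data or visits are needed.
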